4.4. Secondary Endpoints Analysis

4.4.1. 12-month and 18-month incidence of ARIA-E

For the analysis of 52-week ARIA-E incidence, all 4 scheduled MRIs (weeks 4, 12, 24, 52) and unscheduled MRI data as well as treatment-emergent cluster data will be used first to obtain descriptive statistics including total number and proportion of patients with ARIA-E in 1-year in AACQ and by treatment arm.

Like the method for analyzing the primary endpoint, a Bayesian logistic regression will be applied before answering whether relative risk reduction of ARIA-E in 52 weeks is significant comparing the dosing skip arm with standard dosing arm, or comparing the titration arm with standard dosing arm, or comparing the Cmax arm with standard dosing arm. A diffuse prior will be used for each slope parameter in this Bayesian logistic regression model and a mixture prior for the intercept parameter will be elicited from 52-Week ARIA-E outcome in AACI-Addendum 9 study. The probability that one alternative dosing arm has a minimum of 20% risk reduction in ARIA-E in one year compared to the standard dosing arm will be derived from each of 3 simulated posterior distributions in relative risk reductions. In addition, the sensitivity analyses proposed in Section 4.3.3 will be used for 52-week analysis of ARIA-E.

All scheduled postbaseline MRIs (weeks 4, 12, 24, 52, and ED) and unscheduled MRI data as well as treatment-emergent cluster data will be analyzed for ARIA-E events up to Week 76 using the framework in Section 4.3.2 or following the descriptions for the analysis of 1-year incidence of ARIA-E.

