#### **Early discontinuation**

If a participant discontinues the study before Visit 25, perform ED assessments. After the ED Visit, the participant proceeds to Period III to complete the follow-up visit, if possible.

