MRI of the brain				X							X		See Section 8.2.7.1 for MRI sequence details for each visit. Unscheduled MRIs may be performed at the discretion of investigator. ED Visit: Conduct only if ED occurs more than 6 wk from the previous MRI.
Additional Efficacy Measures													
Amyloid PET scan				X						X	X		ED Visit: Conduct only if ED occurs after 3 or more months from the last amyloid PET scan.
Randomization and Dosing													
Register visit with IWRS	X	X	X	X	X	X	X	X	X	X	X	X	
Dispense study intervention using IWRS	X	X	X	X	X	X	X	X	X				
Administer study intervention	X	X	X	X	X	X	X	X	X				The participant must be observed for a minimum of 30 min following the end of each infusion.  Dosing intervals must be more than 21 days apart.

Abbreviations: AE CRF = AE case report form; BP = blood pressure; C-SSRS = Columbia-Suicide Severity Rating Scale; ED = early discontinuation; IWRS = interactive web-response system; IV = intravenous; MMSE = Mini Mental State Examination; MRI = magnetic resonance imaging; PET = positron emission tomography; Q2W = every 2 weeks; sTREM2 = soluble triggering receptor expressed on myeloid cells 2.

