#### Phase 2 Study AACG ARIA events

Study AACG was a Phase 2, double-blind, placebo-controlled study in participants with early symptomatic AD with intermediate brain tau burden. In Study AACG, ARIA (-E, -H, or both) was observed in a higher percentage of participants treated with donanemab, compared to participants treated with placebo. A majority of ARIA-E and ARIA-H events were first observed within 12 weeks of treatment initiation, with most events observed by 24 weeks.

ARIA-E occurred in 26.7% of participants treated with donanemab, with 6.1% of cases being symptomatic. Symptoms associated with ARIA-E included, but were not limited to, worsening of headache, altered mental status, confusion, and difficulty expressing themselves. Serious symptomatic ARIA-E requiring hospitalization occurred in 1.5% of participants treated with donanemab.

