# 7.1. Discontinuation of Study Intervention

When necessary, a participant may be permanently discontinued from study intervention. If study intervention is permanently discontinued, the participant should remain in the study for safety evaluations and biomarker collection, as shown in the SoA.

A participant may be permanently discontinued from study intervention if

- the participant or participant's designee requests to discontinue the study intervention
- the participant requires an excluded treatment
- the participant answered "yes" to Question 4 or Question 5 on the "Suicidal Ideation" portion of the C-SSRS
- the participant answered "yes" to any of the suicide-related behaviors on the Suicidal Behavior portion of the C-SSRS
  - A psychiatrist or appropriately trained professional may assist in the decision to discontinue the participant
- in the opinion of the investigator, the participant should permanently discontinue the study intervention for safety reasons or for severe noncompliance to the study protocol, and
- ARIA (See Sections 7.1.2 and 8.3.3.1 for details).

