# 7.2. Participant Discontinuation/Withdrawal from the Study

Discontinuation is expected to be uncommon.

A participant may withdraw from the study

- at any time at the participant's own request for any reason or without providing any reason
- at the request of the participant's designee, for example, parents or legal guardian
- at the discretion of the investigator for safety, behavioral, compliance, or administrative reasons
- if enrolled in any other clinical study involving an investigational product, or enrolled in any other type of medical research judged not to be scientifically or medically compatible with this study
- if the participant, for any reason, requires treatment with a therapeutic agent that is prohibited by the protocol and has been demonstrated to be effective for treatment of the study indication. In this case, discontinuation from the study occurs prior to introduction of the new agent

• if the participant requires a ferromagnetic implant or insertion of a cardiac pacemaker that is not MRI compatible.

At the time of discontinuing from the study, if possible, the participant will complete procedures for an early discontinuation visit and follow-up, as shown in the SoA. If the participant has not already discontinued the study intervention, the participant will be permanently discontinued from the study intervention at the time of the decision to discontinue the study.

If the participant withdraws consent for disclosure of future information, the Sponsor may retain and continue to use any data collected before such a withdrawal of consent. If a participant withdraws from the study, the participant may request destruction of any samples taken and not tested, and the investigator must document this in the site study records.

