4.6.6. Amyloid-Related Imaging Abnormalities (ARIA)

ARIA incidence was discussed in Section 4.3, Section 4.4.1, and Section 4.4.3. Severity of ARIA events was covered in Section 4.4.3.

Unless otherwise specified, safety analyses of ARIA events are based on centrally read MRI findings from both scheduled and unscheduled visits. Where applicable, ARIA-E summaries will be presented for symptomatic and asymptomatic ARIA-E. ARIA-H summaries will be presented by ARIA-H microhemorrhage and ARIA-H superficial siderosis. Macrohaemorrhage will be described separately and will not be included in the ARIA-H category.

An overview of ARIA incidence by treatment arm from safety analysis set will be presented using frequency and percentage of patients with any ARIA (ARIA-E or ARIA-H), ARIA-E, and ARIA-H as defined by safety MRIs or treatment-emergent AE clusters. The proportion of the patients with serious adverse events of ARIA, ARIA-E, and ARIA-H with or without ARIA-E will be summarized via treatment arm. The frequency and percentage of ARIA-E will be further

broken out by asymptomatic vs. symptomatic and by APOE genotype. The frequency and percentage of subjects with ARIA-H microhemorrhage, ARIA-H superficial siderosis, and macrohemorrhage will be further broken out by APOE genotype. A sensitivity analysis of overview of ARIA incidence will be performed utilizing per-protocol analysis set.

A severity shift table of ARIA-E, ARIA-H microhemorrhage, and ARIA-H superficial siderosis severity from baseline to Week 76 by visit and by treatment arm will be presented.

To investigate the onset of the first ARIA-E or ARIA-H event among different dosing regimens, Kaplan-Meier plots will be presented using safety analysis set. Besides Kaplan-Meier plots, histograms of the onset of the first ARIA-E or ARIA-H based on safety MRI may be provided to visually inspect timing of the first ARIA event across treatment arms.

From safety analysis set, mean and median duration before the resolution of ARIA-E or the mean and median duration of ongoing ARIA-E events for each dosing regimen will be derived.

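### ARIA-E incidence is modelled to Week 76, but no MRI is scheduled after Week 52 apart from a conditional early-discontinuation scan, so the Week 76 figure is a lower bound close to the Week 52 result

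*SAP*

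**What the plan says.** SAP 4.4.1 covers 12-month and 18-month ARIA-E incidence. Its last paragraph states "All scheduled postbaseline MRIs (weeks 4, 12, 24, 52, and ED) and unscheduled MRI data as well as treatment-emergent cluster data will be analyzed" and continues "for ARIA-E events up to Week 76 using the framework in Section 4.3.2 or following the descriptions for the analysis of 1-year incidence". The framework in SAP 4.3.2 is the Bayesian logistic regression for the primary endpoint, which yields posterior relative risk reductions and the probability that each is at least 20%.

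The imaging schedule ends earlier. The Schedule of Activities (Protocol 1.3.3) and the MRI sequence table (Protocol 8.2.7.1) both place the last routine scan at Visit 19 (Week 52). None is scheduled at Visit 25 (Week 76) or Visit 801. The one later scheduled scan is at early discontinuation, and it is conditional: "ED Visit: Conduct only if ED occurs more than 6 wk from the previous MRI". Dosing visits run to Week 72.

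The ED visit is for those who leave the study ("If a participant discontinues the study before Visit 25, perform ED assessments", Protocol 1.3), and its procedures are done "if possible" in the sense of Protocol 7.2: "At the time of discontinuing from the study, if possible, the participant will complete procedures for an early discontinuation visit and follow-up". Those who only stop drug stay on the ordinary schedule: "If study intervention is permanently discontinued, the participant should remain in the study for safety evaluations and biomarker collection, as shown in the SoA" (Protocol 7.1).

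SAP 4.6.6 also plans a shift table of ARIA "severity from baseline to Week 76 by visit and by treatment arm will be presented". The objectives tables list ARIA-E incidence at Weeks 24 and 52 only, and SAP 4.1 describes the Bayesian analysis for those two times.

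**The concern.** Protocol 2.2 describes ARIA as usually without symptoms, and says that asymptomatic ARIA may be picked up by routine MRI. After Week 52 there is no routine MRI for anyone who remains in the study. A first ARIA-E in that period enters the data only through an unscheduled scan, an ED scan or an adverse event report. The logistic model has a yes/no outcome and no term for whether a participant was imaged, so no detected event is the same as no event.

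At stake is a posterior relative risk reduction labelled Week 76 that could be set beside the Week 24 and Week 52 results as if ascertainment were the same. It would mostly repeat the Week 52 comparison and say little about whether the alternative regimens prevent ARIA-E or only delay it. SAP 4.4.1 also names no historical source for a Week 76 intercept prior, although it names one for Week 52.

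**Working it through.** **The plan's own figure.** The documents give none for Week 76. The only simulated result, 92.7% power in SAP 5, concerns Week 24. It reproduces at 92.9% (180 per arm, 10,000 simulated trials) if 4 is read as a variance and 30.19 as a precision. It does not bear on Week 76.

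**Imaging.** Scheduled MRIs between Weeks 52 and 76 for a participant who stays: 0. An ED visit within 6 weeks of a Week 52 scan needs no MRI, which is 6/24 = 25% of the window.

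**Inputs**
- p52, incidence by Week 52: 18.5% (standard) and 11.1% (alternative). These are the Week 24 planning rates in SAP 5; carrying them to Week 52 is an assumption.
- L, first ARIA-E in Weeks 52-76 among those event-free at Week 52: assumed 0.5% to 4%, equal across arms.
- s, share of late events detected in completers, taken as the symptomatic share. Protocol 2.2 says "ARIA-E occurred in 26.7% of participants treated with donanemab, with 6.1% of cases being symptomatic". That is 6.1% as worded, or 6.1/26.7 = 22.8% if 6.1% refers to participants. Applying a Phase 2 share to the late period is an assumption.
- d, dropout in Weeks 52-76: assumed 10%, with dropouts at risk for half the window on average.
- e, detection at ED: 1 - 0.25 = 0.75, assuming uniform exit times, every ED visit completed and nothing missed by the scan.

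**Formulas**
- True Week 76 incidence = p52 + (1 - p52) × L
- Observed = p52 + (1 - p52) × [(1 - d) × L × s + d × (L/2) × e]
- Relative reduction (RRR) = 1 - alternative/standard

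The share of late events detected is (1 - d)s + (d/2)e. This is 0.9 × 0.061 + 0.05 × 0.75 = 9% or 0.9 × 0.228 + 0.05 × 0.75 = 24%.

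**Worked case, L = 2%, s = 6.1%**
- True: standard 0.185 + 0.815 × 0.02 = 0.2013; alternative 0.111 + 0.889 × 0.02 = 0.1288; RRR 36.0%.
- Bracket: 0.9 × 0.02 × 0.061 + 0.1 × 0.01 × 0.75 = 0.00185.
- Observed: standard 0.185 + 0.815 × 0.00185 = 0.1865; alternative 0.111 + 0.889 × 0.00185 = 0.1126; RRR 39.6%.

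| Assumed L | True RRR | Observed RRR (s = 22.8% to 6.1%) | Overstatement, points |
|---|---|---|---|
| 0.5% | 38.9% | 39.7% to 39.9% | about 1 |
| 1% | 37.9% | 39.5% to 39.8% | about 2 |
| 2% | 36.0% | 39.0% to 39.6% | 3 to 4 |
| 4% | 32.6% | 38.0% to 39.2% | 5 to 7 |

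The RRR at Week 52 under these rates is 1 - 11.1/18.5 = 40%, so the observed Week 76 value stays within 2 points of it in every row.

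**Differential dropout.** The largest shift is at L = 4%, s = 6.1%. With equal dropout the observed RRR is 39.2%. With 15% in the standard arm and 5% in the alternative it is 39.7%; reversed, 38.7%. The shift is 0.5 point either way.

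**Dependence on equal late incidence.** Let late incidence also be 40% lower in the alternative arm (2% against 1.2%). The true RRR is 1 - (0.111 + 0.889 × 0.012)/0.2013 = 39.6%. The alternative arm's bracket is 0.9 × 0.012 × 0.061 + 0.1 × 0.006 × 0.75 = 0.00111, so the observed RRR is 1 - (0.111 + 0.889 × 0.00111)/0.1865 = 40.0%. The overstatement falls to about 0.4 point.

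**The case against.** The best defence is that little depends on this analysis. Week 76 ARIA-E is not an endpoint, the success rule is tied to Week 24, and SAP 4.4.1 lists its scans openly. Protocol 2.2 reports that most ARIA events in the Phase 2 study were seen by Week 24, so few first events may remain after Week 52. Detection in completers is also wider than symptoms alone: investigators may order unscheduled MRIs, repeat scans are recommended while ARIA is present, and adverse event clusters count. All of this stands. It limits the size and importance of the problem, but does not make the Week 76 incidence complete.

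A reader might go further and infer that dropouts are fully examined while completers are not, so that discontinuation drives a biased 18-month comparison. Setting 6% to 23% detection in completers against 100% at ED would suggest a 4- to 16-fold contrast. The documents do not support that. The ED scan is not required within 6 weeks of the previous MRI, is done only where possible, and is a single scan that can miss ARIA-E already resolved; dropouts also leave partway through the window. Unequal dropout has little effect in the calculation above.

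It is also fair that ending the SAP 4.6.6 shift table at Week 52 would discard real severity data from ED and unscheduled scans.

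**Conclusion.** The concern holds as one of under-ascertainment. Late asymptomatic ARIA-E in participants who stay in the study is largely unobserved, so a modelled Week 76 incidence is a lower bound and its relative reduction is pulled towards the Week 52 value. That much follows from the schedule and the protocol's own description of ARIA.

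The size does not follow from the documents. The overstatement of about 1 to 7 points depends on the assumed Week 52 rates, the assumed late incidence, its equality across arms, and the Phase 2 symptomatic share. If late incidence falls in proportion to early incidence, the distortion of the comparison nearly disappears, although the incidence itself is still too low. A demonstrated bias between arms, or one driven by discontinuation, should not be claimed. The primary analysis and the Week 52 secondary analysis are not affected.

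**What to change.** Change the SAP wording in two places.

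- **SAP 4.4.1:** end the modelled ARIA-E incidence and its posterior relative risk reduction at Week 52, the last listed ARIA-E endpoint. Report Weeks 52-76 descriptively as detected ARIA-E, by arm and by route (ED MRI, unscheduled MRI, adverse event cluster), and state that no routine MRI was done in this period.
- **SAP 4.6.6:** keep the severity shift table to Week 76, with a note that entries after Week 52 come only from ED or unscheduled scans.

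The cost is one modelled analysis that is not an endpoint. No scans are added and no endpoint changes.

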4.4.2. Amyloid plaque deposit

Participants' brain amyloid deposition will be measured by amyloid PET imaging at visits of screening, 24, 52 and 76 weeks. The frequency and percentage of subjects who achieved amyloid PET clearance (< 24.1 centiloids) in AACQ will be reported. And the count and percentage of subjects who meet dose stopping criteria either due to amyloid < 11 centiloids on one occasion or amyloid between 11 and 25 centiloids on two consecutive measurements will be presented at Week 24, Week 52, or Week 76.

The change from baseline to the post-baseline visit of the amyloid imaging centiloid will be evaluated using a MMRM (mixed model repeated measures) model which includes the fixed effects of treatment arm, time, treatment arm-by-time interaction, baseline age, baseline amyloid level, and baseline amyloid-by-time interaction. Treatment arm, time, as well as treatment arm-by-time interaction are the categorical effects and baseline age, baseline amyloid level, as well as baseline amyloid-by-time interaction are continuous effects. The within-patient covariance matrix of the MMRM is an unstructured one with no assumption made about the variances and covariances. If the unstructured covariance structure matrix results in a lack of convergence, the following tests will be used in sequence:

- heterogeneous Toeplitz covariance structure
- heterogeneous autoregressive covariance structure
- heterogeneous compound symmetry covariance structure
- compound symmetry covariance structure

The Kenward-Roger approximation will be used to estimate the denominator degrees of freedom.

The difference in mean change in the amyloid plaque level between treatment arms at 24, 52, and 76 weeks from baseline will be obtained through the least squares (LS) method. Its associated SE (standard error), 95% of confidence interval, and *p*-value derived from *t* test statistic will be reported as well.

The amyloid PET analysis described above will be based on the EES. A sensitivity PET analysis will be conducted using the per-protocol analysis set.

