# **6.3.** Assignment to Study Intervention

#### Randomization

All participants will be centrally assigned to randomized study intervention using an IWRS. Before the study is initiated, the login information and directions for the IWRS will be provided to each site.

Participants will be randomly assigned to 1 of 4 treatment groups in a 1:1:1:1 ratio.

Participants will be stratified at baseline by amyloid PET scan results ( $\geq$ 24.1 and <54 centiloids;  $\geq$ 54 and <79 centiloids;  $\geq$ 79 and <107 centiloids;  $\geq$ 107 centiloids) and *APOE* genotype (heterozygous carrier, homozygous carrier, and noncarrier).

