4.1. General Considerations

As 4 donanemab dosing regimens including the standard one are available for Study AACQ, any safety or biomarker analysis will involve 3 comparisons: 1) dose skipping vs. standard dosing; 2) titration vs. standard dosing; 3) Cmax (concentration maximum) vs. standard dosing.

Safety analyses will include subjects who are randomized to study treatment and who take at least 1 dose of treatment. Subjects will be analyzed according to the treatment arm to which they were assigned.

Unless otherwise specified, analyses for ARIA events are based on MRI findings or AE (adverse events) reporting. ARIA safety analyses will cover both ARIA-E and ARIA-H events by Week 24 as well as by Week 52. Bayesian logistic regression method is proposed to obtain a posterior distribution regarding relative risk reduction in ARIA-E or ARIA-H at Week 24 or 52 for each of 3 comparisons mentioned above. The details of logistic regression model, prior elicitation, and computation for the posterior distribution will be presented in Section 4.3.2. From each derived posterior distribution of RD_{21} , RD_{31} , and RD_{41} , summary statistics will be reported which include posterior mean, posterior median, posterior mode, a 2-sided equal-tailed 95% posterior interval (often cited as credible interval in Bayesian literature), and a posterior probability of achieving a minimum of 20% relative risk reduction in ARIA-E.

Frequentist methods will be used for the rest of the study objectives. All frequentist tests will be conducted at a 2-sided alpha level of 0.05; 2-sided confidence intervals (CIs) will be displayed with a 95% confidence level.

Unless otherwise noted baseline is defined as the last measurement prior to dosing. When change from baseline is assessed, subjects will only contribute to the analysis if both a baseline and a post-baseline measurement are available. Endpoint is the last non-missing post-baseline measurement within the time period for the given analysis.

To allow for evaluation of the primary and secondary hypotheses at 24 and 52 weeks, database locks and the assessments of corresponding primary and secondary objectives are expected to occur after all participants in the Safety Analysis Set have had the opportunity to complete visits 12 and 19 including PET and MRI assessments. The sponsor may choose not to have a separate database lock after visit 19 and wait to perform the analyses for 52-week data until the final database lock.

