4.3.2. Main analytical approach

The number of ARIA-E events and the percentage of participants by treatment arm with any occurrence of ARIA-E events will be tabulated. The percentage of any occurrence of ARIA-E events is equivalent to ARIA-E incidence proportion. The primary analysis will use a Bayesian logistic regression model to estimate relative risk reduction in ARIA-E between alternative donanemab dosing regimen and standard donanemab dosing regimen given ARIA-E data up to Week 24.

The logistic regression model will include categorical effects of treatment arm, APOE e4 genotype, baseline presence of microhemorrhage, baseline presence of superficial siderosis, and baseline amyloid level. Treatment arm is a multinomial variable with 4 levels. APOE e4 genotype status has 3 levels: heterozygous carrier, homozygous carrier, and non-carrier. As participants with ≤4 microhemorrhages at baseline are eligible to enroll into this study, the model needs to adjust for baseline presence of microhemorrhage which is a binary predictor. The proposed model will also assess the impact of baseline presence of superficial siderosis because the study allows enrollment of eligible subjects with 1 area of cortical superficial siderosis. Baseline amyloid values are divided into terciles.

An integral part of Bayesian analysis is the formulation of prior distributions for regression coefficients. A diffuse prior will be assigned to all slope parameters to reflect the impact of the alternative dose regime and the effect of baseline covariates solely based on the data collected from the study. For the intercept parameter, a mixture prior will be using information on ARIA-E rates of the standard donanemab dosing regimen by 24 weeks from AACI – Addendum 9 study. The mixture prior will have a diffuse and an informative component. However, the informative component will have much less variability than the diffuse component. Both prior means are equal to log odds of the ARIA-E incidence in AACI-Addendum 9 study at Week 24. One normal prior has much less variability compared to another normal prior that is relatively flat. 50% weight will be assigned to each component of the mixture a priori.

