4.7. Interim Analysis

An external Data Monitoring Committee (DMC) is authorized to evaluate results from unblinded interim analyses for the assessment of safety and futility and to recommend any modifications to the study (including stopping the study). Operational details and the decision rules will be provided in the DMC charter.

The DMC will have the responsibility to review accumulating unblinded study data and make recommendations to protect the safety of patients. The DMC will consist of a minimum of 3 members, including a physician with expertise in AD and a statistician. All members will be external to the Sponsor. The approved DMC charter enumerates the roles of the DMC members, the frequency with which it meets, and the structure of their meetings. Study sites will receive information about interim results ONLY if relevant for the safety of their patients.

For safety reviews, the DMC will receive data monitoring results that will include at least the following:

- Demographic characteristics of enrolled subjects
- Adherence to assigned treatment regimen
- Serious adverse events (SAEs)
- Non-serious adverse events
- Adverse events necessitating unblinding at the site or by the sponsor
- Vital signs data
- Central lab data
- Safety MRI data
 - Number of patients with significant treatment-emergent MRI findings, especially Amyloid Related Imaging Abnormalities (ARIA) events such as vasogenic edema or microhemorrhage
 - o Listing of all significant treatment-emergent MRI findings
 - o For patients with ARIA events, standard listings of medical history, concomitant medications, adverse events, baseline demographics
- C-SSRS data

At least 1 interim safety analysis may be conducted for the entire AACQ Study. Operational details and a quantitative framework to provide information for these decisions will be documented in interim analysis Statistical Analysis Plan.

5. Sample Size Determination

Approximately 800 participants will be randomly assigned to 1 of 4 treatment arms in a 1:1:1:1 ratio. It is hypothesized here that in each treatment arm, 10% of participants will not reach primary outcome lock. Below we showed that 720 participants who completed visit 12 can provide more than 80% power to demonstrate that there is over 80% probability that at least one of the alternative dosing regimens will reduce relative risk of ARIA-E by at least 20% compared to the standard dosing regimen.

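### The amyloid PET repeated-measures model omits APOE genotype, one of the two stratification factors, without a stated reason; if APOE predicts amyloid change, the reported intervals are slightly too wide

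*SAP*

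**What the plan says.** Protocol 6.3 names two stratification factors. The first is amyloid burden in four centiloid bands ("Participants will be stratified at baseline by amyloid PET scan results"). The second is APOE "genotype (heterozygous carrier, homozygous carrier, and noncarrier".

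The PET model in SAP 4.4.2 has these fixed effects: "treatment arm, time, treatment arm-by-time interaction, baseline age, baseline amyloid level, and baseline amyloid-by-time interaction". The SAP adds that "baseline age, baseline amyloid level, as well as baseline amyloid-by-time interaction are continuous effects". So one stratification factor is in the model, in a finer form than the randomisation bands and with its own time interaction. The other is absent.

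The primary ARIA-E model in SAP 4.3.2 carries both: "The logistic regression model will include categorical effects of treatment arm, APOE e4 genotype, baseline presence of microhemorrhage", with baseline amyloid in terciles further along the same list.

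SAP 4.4.2 reports, for Weeks 24, 52 and 76, the difference in mean change with its standard error, 95% confidence interval and p-value. SAP 4.1 sets the level: "All frequentist tests will be conducted at a 2-sided alpha level of 0.05". The one planned PET sensitivity analysis repeats the model on the per-protocol set.

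**The concern.** An analysis should normally adjust for the factors used to stratify randomisation. Stratifying balances the arms on APOE by design. If APOE also predicts the outcome and is left out, its contribution stays in the model's error variance although it cannot separate the arms. The reported standard error is then larger than the true sampling spread of the treatment difference.

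Wider intervals matter here under either reading of the PET objective. Protocol 9.3.3 plans a non-inferiority test on amyloid change, and an interval that is too wide makes preserved lowering harder to show. SAP 4.4.2 reports a difference with a p-value, and an overstated standard error makes a real loss of lowering harder to detect. Nothing planned would show whether leaving APOE out makes a difference.

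**Working it through.** **No plan figure to reproduce.** The documents state no standard deviation, effect size, margin or power for the PET comparison. They also give no association between APOE and amyloid change. Its strength is therefore an assumption, shown as a range that includes zero.

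**Inputs from the documents.** SAP Section 5: "Approximately 800 participants will be randomly assigned to 1 of 4 treatment arms in a 1:1:1:1 ratio", and "It is hypothesized here that in each treatment arm, 10% of participants will not reach primary outcome lock". That gives 800 × 0.90 = 720 participants, or 180 per arm, at Week 24.

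**Assumed input.** R² is the share of the residual variance in amyloid change, after the terms already in the model, that APOE explains.

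**Step 1: size of the excess.** Adding APOE multiplies the reported standard error by √(1 − R²). Leaving it out therefore makes intervals too wide by the factor 1/√(1 − R²). The ratio does not depend on the standard deviation or on the number of participants.

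| Assumed R² | √(1 − R²) | SE reduction if APOE is added | Excess width if it is omitted |
|---|---|---|---|
| 0 | 1.000 | 0% | 0% |
| 0.01 | 0.995 | 0.5% | 0.5% |
| 0.05 | 0.975 | 2.5% | 2.6% |
| 0.10 | 0.949 | 5.1% | 5.4% |

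**Step 2: reported error against true error.** Trials of 720 participants were simulated with blocks stratified by APOE and the four amyloid bands. A single-visit analysis of covariance was fitted with and without APOE, 3,000 runs per R². The assumed values were a residual SD of 25 centiloids, an APOE mix of 30/53/17% and a normal baseline amyloid distribution (mean 90, SD 30). As a check, the reported SE without APOE should be 25 × √(2/180) = 2.64.

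| R² | Reported SE without / with APOE | True sampling SD without / with APOE | 95% CI coverage without APOE |
|---|---|---|---|
| 0 | 2.63 / 2.63 | 2.61 / 2.61 | 95.1% |
| 0.05 | 2.64 / 2.57 | 2.62 / 2.61 | 95.0% |
| 0.10 | 2.64 / 2.50 | 2.52 / 2.52 | 95.7% |

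Simulation error in the sampling SD is about 2.62/√(2 × 3000) = 0.03, so the R² = 0.05 row cannot resolve a 2.5% effect. The R² = 0.10 row shows the mechanism. The estimate varies by the same 2.52 with or without APOE, because stratification has already balanced it. Only the reported SE differs, and without APOE it is too large.

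**Step 3: power.** Suppose a comparison has 80% power when planned with the SE that omits APOE. With APOE the power is Φ[(1.960 + 0.842)/√(1 − R²) − 1.960], which is 80.4%, 82.0% and 84.0% at R² = 0.01, 0.05 and 0.10. The real gain is smaller, because the model without APOE already benefits from the balance. At R² = 0.10 its actual power is Φ(0.842/0.949) = Φ(0.887) = 81.2%, against 84.0% with APOE.

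**The case against.** The case for leaving the model alone has real force.

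- **No contradiction.** Protocol 9.3.3 lists no covariates for the PET analysis. The blood-biomarker model in SAP 4.5.2 also omits APOE. APOE has an evident place in the primary model, because Protocol 2.2 links carriage to ARIA risk. All of this stands, though none of it is a stated reason for omitting a stratification factor.
- **The premise is undocumented.** The documents tie APOE to ARIA, not to amyloid lowering. Zero effect is as compatible with them as any value above. This stands, and it is why the size is conditional.
- **The error is on the safe side.** No bias or inflation of the type I error appears with complete data. This also stands. Conservative is not the same as costless, however, where a wide interval can hide a loss of amyloid lowering.

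Three stronger readings are tempting and are not supported:

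- A reader might infer that the standard errors ignore the stratification. They do not: baseline amyloid, the other factor, is in the model.
- A reader might infer that the treatment estimates are materially less precise, and convert the excess width into lost participants. Step 2 shows that the true spread is essentially unchanged. Any such conversion would also rest wholly on an assumed R².
- A reader might infer that omitting APOE undermines the missing-at-random assumption, through dropout caused by ARIA. That is speculative. Protocol 7.1 keeps participants who stop treatment in the study. The schedule of activities provides a PET scan at early discontinuation if at least three months have passed since the last one. The argument also needs APOE to predict amyloid change, the same unstated premise.

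**Conclusion.** The omission is plain from the documents: the PET model adjusts for one of the two stratification factors and leaves out the other without explanation. The consequence is conditional and small. Intervals are too wide by about 0.5% to 5.4% for an assumed R² of 1% to 10%, and by nothing if APOE is unrelated to amyloid change given the terms already in the model. The direction is conservative.

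The ratio in Step 1 depends only on R². The simulation also rests on the assumed SD, APOE mix and baseline distribution, uses one visit instead of the full repeated-measures model, and has no missing data. Amyloid change is a secondary endpoint, and the documents do not rank it above the other secondary endpoints. The severity is minor. The change is worth making because it is nearly free.

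**What to change.** In SAP 4.4.2, add APOE genotype (heterozygous carrier, homozygous carrier, noncarrier) as a categorical fixed effect in the PET model. Do so for both the evaluable efficacy set and the per-protocol set. Preferably add APOE-by-time as well. Baseline amyloid already has a time interaction, and a main effect alone would force the same APOE effect at Weeks 24, 52 and 76.

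The main effect costs 3 − 1 = 2 degrees of freedom. The interaction with three visits adds 2 × (3 − 1) = 4, for a total of 6. Genotype is needed to randomise and its sample is mandatory (Protocol 8.6), so no new data are required.

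If the sponsor prefers to keep the present model, the SAP should give the reason and add a sensitivity analysis that includes APOE. Either change should be fixed before the treatment codes are opened for the PET analysis.
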